**Abstract:**

Because curative therapy for multiple myeloma is not yet available, the treatment goal is to produce lengthy asymptomatic disease remissions. High dose chemotherapy with autologous hematopoietic stem cell transplant (AHSCT) provides optimal remission outcomes, and is the current standard of care for transplant eligible patients. However, some patients experience early relapse. One possible explanation for early relapse is poor immune recovery after high dose chemotherapy given before AHSCT. Harvesting an autologous transplant graft product from circulating blood is facilitated by administration of granulocyte colony stimulating factor (G-CSF) to mobilize large numbers of hematopoietic stem cells into the circulation. The cells are collected from the blood with apheresis and stored until the transplant. Our preliminary studies show that immune suppressor cells are also mobilized and collected in the graft product. Depletion of these suppressor cells in the graft before transplant provided enhanced T-cell reactivity to allogeneic antigens and lymphocyte homeostatic expansion. The hypothesis is that depleting majority of immune suppressive cells from G-PBSC graft in vitro in the setting of AHSCT will tip the balance towards accelerated lymphocyte expansion in-vivo, which will be reflected in high ALC numbers on day 15 ( $>500/\mu\text{l}$ ). The goal is to achieve this depletion via selection and infusion of CD34+ cells, thereby eliminating MDSC's and T-reg's which have an immunosuppressing effect on immune reconstitution. This pilot randomized Phase II trial (10 subjects per arm) will compare immune reconstitution following transplantation of an autologous mobilized graft product to reconstitution following transplantation of a mobilized graft product followed by an autologous lymphocyte infusion collected prior to G-CSF mobilization. All subjects will receive tetanus vaccines pre and post-transplant. The primary end point will be tetanus vaccine immune responses post-transplant.

**Schema:**

As shown in the schema above:

- 1- Subjects in all groups will receive tetanus vaccine 7-10 days prior to mobilization.
- 2- Subjects in group 1 will have mononuclear cells collected and frozen 7-10 days after tetanus vaccination pre-transplant. These subjects will then receive a CD34+ selected graft on day 0 and autologous donor lymphocyte infusion (DLI) on day +7.
- 3- Subjects in group 2 will receive a standard G-CSF mobilized graft on day 0 without any DLI post-transplant.
- 4- Subjects in all groups will receive G-CSF as subcutaneous injections daily (10 µg/kg) x 5 days starting on day -11 (following the DLI pheresis in the experimental group). Subjects will receive one dose of plerixafor, a stem cell mobilizer, followed by pheresis on the next day to collect G-PBSC graft, with the goal of  $> 6.0 \times 10^6$  CD34+ cells/kg.
- 5- On day of G-PBSC pheresis, the graft in group 2 will be analyzed for CD34, lymphocyte content, and T-reg and MDSCs (cell differential and flow cytometry). Then it will be processed and frozen as per local institutional standards.
- 6- The stem cell product will start to be washed while waiting for the CD34+ content to be known. CD34+ stem cells will then be selected out of the G-PBSC mobilized graft the same day using clinical grade CD34+ magnetic beads and Clinimacs device from Miltenyi as per manufacturer's instructions and as described below. The CD34 content will be analyzed before freezing in liquid nitrogen.
- 7- The subjects in all groups will receive high dose chemotherapy Melphalan at 200 mg/m^2 on day -1.

8- On day 0, subjects in group 1 will receive the thawed CD34+ stem cell graft, while subjects in the group 2 will receive the standard thawed G-PBSC graft. Transplanted CD34+ stem cell dose both groups will be in the range of 2-10 X 10^6/Kg body weight.

9- On day +7 post-transplant, the stored autologous donor lymphocyte product in group 1 will be thawed and infused back to the subjects.

10- **No planned G-CSF post-transplant** (unless medically deemed necessary due to slow engraftment by day 15)

11- Subjects will be followed closely in the hospital until engraftment and resolution of all transplant related toxicities.

12- Subjects will be closely evaluated for any trial related adverse events, specifically: delayed engraftment, auto-immune side effects (autologous graft versus host disease), and infections.

13- At day +15(+/-3) and day +60 (+/-3) post-transplant, all subjects will receive tetanus vaccines.

14- At days + 30(+14), +70(+14), +100(+/-10), and 180(+/-10) post-transplant subjects will undergo immune evaluation for tetanus vaccine responses.

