## **Section 1.0 Objectives:**

### **Hypotheses**

1. The abundance of immune suppressive cells in G-PBSC grafts results in poor immune reconstitution post AHSCT, leading to higher risk for infection and myeloma relapse.
2. Depletion of immune suppressor cells from G-PBSC graft will allow a robust *in vivo* expansion of the adoptively transferred lymphocytes as well as a robust recovery of antigen specific tetanus immune response post-transplant compared with the control group.
3. It is safe and feasible to deplete all immune suppressive cells from G-PBSC grafts by positively selecting CD34+ cells from G-PBSC grafts and combining that with an autologous donor lymphocyte infusion product.

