##### **5.1.3 Pre-G-CSF PBMC (DLI) Pheresis**

Seven to 10 days after vaccine, subjects in group 1 will undergo mononuclear leukapheresis to collect and freeze PBMC product for DLI. Subjects will be apheresed for a target blood processed volume of 24-28 liters or as the patient tolerates and per standard UNMC BPF practice. Lymphocyte content of the apheresed product as well as subset analysis will be determined by a cell differential count and flow cytometry.

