#### 5.1.7 Stem Cell lab processing for CD34+ selection

The PBSC pheresed graft is washed initially with PBS containing 5mM EDTA and 0.05% human albumin as per manufacture's standard operating procedure SOP. After reducing the total volume to 95 mls, the anti CD34 antibody (directly conjugated to magnetic micro beads Miltenyi) will be added and incubated for 30 minutes. The cells then washed with Max buffer and attached to Clinimax tubing set. The enriched cells will be cryopreserved with DMSO 7.5%, PBS/HAS 4%/heparin and stored in the gas phase of liquid nitrogen. CD34 content of the final product should be no less than 2 million/Kg body weight.

All subjects in the control group will have the graft absolute lymphocytes quantified (differential count). A sample of the graft will be sent to the stat hematology lab for white cell count and differential. In addition, another sample will be sent for flow cytometry for subset analysis.

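### T-reg and MDSC are measured in the control graft but not in the CD34-selected graft, so the trial cannot show by direct measurement that the experimental arm was infused with fewer suppressor cells

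*Combined protocol and SAP*

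**What the plan says.** The Schema assigns different assays to the two grafts. Item 5 states that "the graft in group 2 will be analyzed for CD34, lymphocyte content, and T-reg and MDSCs". Item 6, on the product that goes through CD34 selection, gives one assay: "The CD34 content will be analyzed before freezing in liquid nitrogen".

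Section 5.1.7 repeats the pattern. The selected product has a single content criterion, "CD34 content of the final product should be no less than 2 million/Kg body weight", with no purity, T-reg or MDSC figure. The next paragraph turns to the other arm: "All subjects in the control group will have the graft absolute lymphocytes quantified". The same paragraph adds that "another sample will be sent for flow cytometry for subset analysis".

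Group 1 also receives a stored lymphocyte product (DLI) on day +7. Section 5.1.3 sets its collection by volume: "Subjects will be apheresed for a target blood processed volume of 24-28 liters or as the patient tolerates". It then asks for a lymphocyte count and a subset analysis by flow, without naming the subsets.

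Hypothesis 3 in Section 1.0 says: "It is safe and feasible to deplete all immune suppressive cells from G-PBSC grafts". The Abstract and Section 5.7.1 speak of depleting the majority rather than all. Section 10 plans no summary or comparison of the cells infused.

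**The concern.** The experimental treatment is a change in what is infused: a graft meant to be low in T-reg and MDSC, plus lymphocytes collected before G-CSF. The cells that should be missing are counted only in the arm where nothing is removed.

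Two things are at stake. First, the depletion part of hypothesis 3, whether read as all or as the majority of suppressor cells, has no direct measurement behind it in the arm where depletion takes place. Second, a tetanus result becomes hard to explain. A null result could mean that selection left suppressor cells behind, that the DLI (drawn from unselected blood) returned some, or that depletion does not help. A positive result could reflect fewer suppressor cells or another part of the package. With 10 subjects per arm and the stated aim of informing later work, that explanation is much of what the pilot can offer.

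**Working it through.** **Plan's own figure.** The plan gives no figure for suppressor cells in any infused product. Its only design figure is the power in Section 10.5: at least 80% for d = 1.36, 10 per arm, two-sided 5%, Mann-Whitney. With the asymptotic relative efficiency 3/π, effective n per arm = 10 × 3/π = 9.55, df = 2 × 9.55 − 2 = 17.1, noncentrality = 1.36 × √(9.55/2) = 2.97, and power = 0.800. An exact Mann-Whitney simulation (20,000 runs) gives 0.783. The stated figure reproduces; this point does not use it.

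**Step 1: which product is assayed for what.**

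| Product | Arm | CD34 | Lymphocytes | T-reg and MDSC | Source |
|---|---|---|---|---|---|
| Graft as infused | 2 | yes | yes | yes | Schema item 5; 5.1.7 |
| Collected graft before selection | 1 | yes | not stated | not stated | 5.1.6 |
| CD34-selected graft as infused | 1 | yes | not stated | not stated | Schema item 6; 5.1.7 |
| DLI product | 1 | not stated | yes | subsets not named | 5.1.3 |

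The flow sentence in Section 5.1.7 does not itself repeat the arm, but it sits in a paragraph that opens with the control group and follows on from that group's lymphocyte count. Schema item 5 agrees with that reading.

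**Step 2: does another planned sample fill the gap?**
- The table in Section 5.1.2 schedules flow on graft-collection day for all subjects, but the section's text makes this peripheral blood. Section 5.7.2 also describes blood samples, and Appendix B lists blood, 10 mL, with no graft aliquot. None of these is the product after selection.
- Post-transplant T-reg and MDSC (secondary objective 2; Section 5.7.2) reflect recovery in the patient as well as what was infused.
- The preliminary data that can be read in Section 2.11 depleted cells with CD33/15 and CD25 reagents, not by CD34 selection, so they do not show what this method leaves behind.

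**Step 3: does CD34 content fix the residual?** Non-CD34 cells infused = CD34 dose × (1 − p)/p, where p is product purity. The CD34 range of 2 to 10 million/kg comes from Section 5.1.9. Purity is not in the documents; 80% to 99% is assumed here.
- At 2 million/kg: p = 0.99 gives 2 × 0.01/0.99 = 0.02 million/kg; p = 0.80 gives 2 × 0.20/0.80 = 0.50 million/kg.
- At 10 million/kg: 0.10 to 2.5 million/kg.

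At a fixed CD34 dose the residual varies by (0.20/0.80)/(0.01/0.99) = 24.75, about 25-fold. These are all non-CD34 cells, of which T-reg and MDSC are an unknown share. CD34 content alone does not determine the residual.

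**Step 4: what the comparison needs.** Suppressor dose in group 1 = selected graft + DLI; in group 2 = graft. Under the plan as written the first term is unmeasured, the second is measured only if the unnamed subsets happen to include T-reg and MDSC, and the third is measured.

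**The case against.** The strongest reply is that positive CD34 selection discards other cells by construction. The protocol itself reports T-cell depletion and severe lymphopenia after CD34-selected grafts (Sections 2.5 and 5.3), and the illustration above puts all residual non-CD34 cells at no more than 2.5 million/kg under the assumed purities. This stands as indirect evidence that the graft is depleted. It is not a measurement, and it does not cover the DLI.

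For the DLI, the plan offers more than a first reading suggests. Section 5.1.2 schedules flow on blood taken just before the lymphocyte collection, and Section 5.7.2 names T-reg and MDSC among its phenotypes. Together with the DLI lymphocyte count, this allows infused T-reg to be estimated. That also stands, as an estimate.

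The worry that lymphocyte dose explains a positive result is partly met too: lymphocytes are counted in the group 2 graft and in the DLI, and only the selected product, where few are expected, lacks a count. A cell-dose table would not separate mechanisms in any case, because the arms differ by a whole package.

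Three stronger readings are tempting but not supported:
- A reader might infer that the primary feasibility objective cannot be answered. Section 1.1 asks about the feasibility and safety of the approach. Day-1 yield against 6 million CD34/kg (5.1.6), final product against 2 million CD34/kg (5.1.7) and engraftment (10.2) are all observable.
- A reader might infer that the primary comparison is compromised. Tetanus responses are measured at the same times in both randomized arms, whatever is known about the products.
- A reader might try to size the problem by variation in DLI dose. The documents supply only the volume target (28/24 = 1.17); anything larger needs assumed counts and collection efficiency. It also concerns a product whose lymphocytes are counted, not the unmeasured selected graft.

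Finally, Section 14.0 refers to a Manual of Operations and a lab manual that are not among the documents. A product assay could be specified there.

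**Conclusion.** The gap is real and limited. In the protocol text, the lymphocyte, T-reg and MDSC panel covers the 10 group 2 grafts and none of the 10 group 1 selected grafts, and the DLI panel names neither cell type. The trial therefore cannot show by direct measurement that group 1 was infused with fewer suppressor cells. This weakens the depletion part of hypothesis 3 and the reading of a null or a positive tetanus result. It does not touch the validity of the randomized comparison, and no effect on that comparison's error rates or power is claimed.

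The weight is moderate: a cheap improvement to a mechanistic measure in an exploratory 20-subject trial. The conclusion rests on reading the flow sentence in Section 5.1.7 as applying to the control group, and on no product assay being specified in manuals outside these documents. The purity range serves only to show that CD34 content does not settle the question.

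**What to change.** - **Schema item 6 and Section 5.1.7:** run the panel already planned for group 2 (differential plus T-reg and MDSC flow) on an aliquot of the group 1 product before and after selection. If a manual already requires this, cite it and correct the text that limits the panel to group 2.
- **Section 5.1.3:** name T-reg and MDSC in the DLI subset panel, with the same marker definitions.
- **Section 10:** add a descriptive table of T-reg, MDSC and lymphocytes infused per kg by arm, with group 1 as selected graft plus DLI and group 2 as graft. A formal between-arm test of the dose difference is not needed.

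Cost: 10 subjects × 1 or 2 aliquots = about 10 to 20 extra flow runs on a product already sampled for CD34, a few cells, some reagent and one table. No treatment changes and no patient procedure is added. The change has to be made prospectively, because without a retained aliquot the composition of a product cannot be recovered once it has been infused.

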## **Section 1.0 Objectives:**

### **Hypotheses**

1. The abundance of immune suppressive cells in G-PBSC grafts results in poor immune reconstitution post AHSCT, leading to higher risk for infection and myeloma relapse.
2. Depletion of immune suppressor cells from G-PBSC graft will allow a robust *in vivo* expansion of the adoptively transferred lymphocytes as well as a robust recovery of antigen specific tetanus immune response post-transplant compared with the control group.
3. It is safe and feasible to deplete all immune suppressive cells from G-PBSC grafts by positively selecting CD34+ cells from G-PBSC grafts and combining that with an autologous donor lymphocyte infusion product.

### **1.1 Primary:**

- 1- To compare the **cellular and humoral** vaccine response post-transplant between the two arms by performing Elisa, and T-cell enzyme-linked immunospot (ELISPOT) assays
- 2- To determine the feasibility and safety of this approach

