## **Section 10.0 Statistical Considerations:**

### **10.1 Primary Objectives**

Given the known lack of vaccine response in the first few months post autologous stem cell transplantation, we intend to look for evidence of vaccine response in the experimental arm via increase in tetanus specific T-cell Elispots and anti-tetanus antibody (Elisa) on days 30, 70, 100 and 180 post-transplant. Given the pilot/explorative nature of this trial and the lack of good pre trial assumptions about vaccine response, we will evaluate the vaccine response by Elisa and Elispot on days 30, 70, 100 and 180 will be compared between groups using a Mann-Whitney test.

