### **10.2 Secondary Objectives**

For the secondary objectives, engraftment, development of any auto immune side effects, and infections will be treated as binary variables. Chi-square tests will be used to compare each of these 3 outcome variables between the two groups, respectively. A Wilcoxon signed-ranks test will be employed to test the change in absolute lymphocyte (ALC), absolute monocyte counts (AMC), immune cells (T cells CD8, CD4), natural killer cells,  $\gamma\delta$  T-cells, T-reg and MDSCs) at days 15 and 30 post AHSCT from the baseline among each group, respectively. Wilcoxon signed-ranks test will be further used to compare the change of change in ALC, AMC and immune cells between the two groups at days 15 and 30 post- AHSCT, respectively.

Generalized linear mixed models will be employed to compare the change pattern of ALC, AMC and immune cells between the two groups over the entire follow up periods. Time to relapse and overall survival will plotted using the methods of Kaplan and Meier and the log rank test will be used to compare the time to event curves between the two treatment groups.

Lastly, as an explorative objective will also be depth of anti-myeloma response as evaluated by the standard IMWG criteria, including the rate of sCR, and subsequent MRD status for the subjects in sCR.

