### **10.5 Sample Size and Power Consideration**

This is exploratory trial with a total sample size of 20 subjects total (10 subjects in each phase II arm). There is no preliminary data on the primary endpoint of the study (baseline tetanus vaccine response early after transplant). However, it is known that vaccine response in general is muted in the first three months post-transplant. We hypothesize to see a wide difference in Elispot values between the two arms. Two-sided two sample t-test is used to for power calculation. The sample size of 20 will achieve a power of at least 80% to detect an effect size of  $d=1.36$  for a Mann-Whitney test comparing two independent groups at the significance level of 5% assuming that the actual distribution is Normal. Because of the exploratory nature of the study, corrections for multiple comparisons will not be performed. Significance for each test will be set at  $P<.05$ .

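### Feasibility and safety are a primary objective, but Section 10.1 gives them no analysis: safety gets only between-arm chi-square tests without intervals, and feasibility has no proportion or denominator

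*Combined protocol and SAP*

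**What the plan says.** Section 1.1 has two primary objectives. The first is vaccine response; the second is "To determine the feasibility and safety of this approach". The third hypothesis in Section 1.0 makes the matching claim: "It is safe and feasible to deplete all immune suppressive cells from G-PBSC grafts".

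The Abstract names one endpoint: "The primary end point will be tetanus vaccine immune responses post-transplant". Section 10.1 follows the Abstract, not 1.1. Its analysis reads "we will evaluate the vaccine response by Elisa and Elispot on days 30, 70, 100 and 180 will be compared between groups using a Mann-Whitney", and it does not mention feasibility or safety.

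The safety outcomes are in Section 10.2: "For the secondary objectives, engraftment, development of any auto immune side effects, and infections will be treated as binary variables". The method is one sentence: "Chi-square tests will be used to compare each of these 3 outcome variables between the two groups, respectively". Section 1.2 lists immune cell recovery, T-reg and MDSC recovery and progression-free survival as secondary, and none of these three outcomes.

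Other sections bear on the objective without analysing it:
- Section 10.4 halts the protocol when more than three experimental-arm subjects have an irreversible, treatment-related grade 3-4 toxicity.
- Section 5.3 holds accrual after three consecutive subjects with low lymphocyte counts at four weeks.
- Section 9 covers grading, recording and committee reporting of adverse events.
- Section 5.1.6 takes subjects who miss the day-1 collection minimum out of the experimental arm, to be treated and followed like group 2, and mentions a separate analysis of them without describing it. Section 5.6 says such subjects are either removed or transferred to arm 2.
- Section 5.1.7 sets a minimum CD34 content for the selected product, and 5.1.10 gives the day +7 infusion.

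**The concern.** A primary objective needs a quantity to estimate and a way to report it. The second one has neither in 10.1, and what 10.2 offers does not fill the gap.

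On safety, a two-sided test of difference asks whether the arms can be told apart. With 10 per arm they usually cannot be, even when the experimental arm does clearly worse. The figure that a later trial needs, the event rate in group 1 with its uncertainty, is not planned. The protocol gives reasons to expect harm: Section 2.5 cites more viral and bacterial infection after CD34-selected autografts, and 5.3 cites severe lymphopenia.

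On feasibility, the gap is wider. The protocol foresees that some subjects in group 1 will not get the experimental product, and it moves them out of the arm. Unless the denominator is fixed as everyone randomised to group 1, those failures can drop out of the result that the objective is meant to deliver.

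**Working it through.** **1. The plan's own figure.** Section 10.5 states at least 80% power for a Mann-Whitney test with 10 per arm, d = 1.36 and two-sided 5%, assuming Normal data. Using the noncentral t with the sample size multiplied by the test's relative efficiency 3/π:
- effective n per arm = 10 × 3/π = 9.55; df = 2 × 9.55 − 2 = 17.1
- noncentrality = 1.36 × √(9.55/2) = 2.97; critical t = 2.11
- power = 80.0%.

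The figure reproduces. It concerns Elispot; the section gives no figure for safety or feasibility.

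**2. What the 10.2 test declares significant.** Inputs: 10 per arm and P<.05 (10.5). For x of 10 against 0 of 10, uncorrected chi-square = 20 × (10x)² / [10 × 10 × x × (20 − x)], and two-sided Fisher P = 2 × C(10,x)/C(20,x).

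| Group 1 v group 2 | Chi-square | P | Fisher P |
|---|---|---|---|
| 3/10 v 0/10 | 18000/5100 = 3.53 | 0.060 | 2 × 120/1140 = 0.21 |
| 4/10 v 0/10 | 32000/6400 = 5.00 | 0.025 | 2 × 210/4845 = 0.087 |
| 5/10 v 0/10 | 50000/7500 = 6.67 | 0.010 | 2 × 252/15504 = 0.033 |

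Three events against none is not significant by either test.

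**3. Power of the 10.2 test.** The documents give no expected rates for these three outcomes, so every pair below is an assumption. Power is the sum of binomial probabilities over all 11 × 11 possible tables with P<.05.

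| Assumed rate, group 1 v group 2 | Uncorrected chi-square | Fisher |
|---|---|---|
| 30% v 2% | 29% | 12% |
| 30% v 10% | 14% | 6% |
| 50% v 20% | 25% | 13% |
| 50% v 10% | 47% | 30% |
| 70% v 10% | 82% | 67% |

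At a 10% control rate, about 80% power by chi-square needs a gap near 60 percentage points. The 2% control rate is the least apt for infection, since Section 2.5 cites first-year VZV risk of 23-50%; the other rows show that the conclusion does not depend on it.

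**4. What intervals would show.** Exact (Clopper-Pearson) two-sided 95% limits:
- 0/10 events: upper limit 1 − 0.025^(1/10) = 31%
- 1/10 events: 0.3% to 45%
- 0/10 in both arms: the Newcombe 95% interval for the difference is −28 to +28 percentage points.

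**5. The feasibility denominator.** Suppose, for illustration, that 2 of 10 subjects randomised to group 1 miss the collection minimum and the other 8 receive both graft and infusion. Over all randomised, feasibility is 8/10 = 80% (95% CI 44% to 97%). Over those who stayed in the arm, it is 8/8 = 100%, with a lower limit of 0.025^(1/8) = 63%. The plan does not say which of these to report.

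**6. The halting rule as a substitute.** Section 10.4 needs at least 4 events. With 10 treated, P(X ≥ 4) is 1.3%, 12%, 35%, 62% and 83% at assumed true rates of 10%, 20%, 30%, 40% and 50%.

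**The case against.** **The plan does not ignore safety.** Section 10.4 is a criterion on the experimental arm inside the statistical section, 5.3 holds accrual, and Section 9 provides grading and committee review. This stands. A reader might infer that the safety objective can be closed only by a non-significant test, or that the sponsor means to read P>.05 as safe. No passage says so, and these provisions count against it. They are monitoring rules, however, and none gives an estimate or interval at the end of the study.

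**The label has little effect.** Section 10.5 applies no multiplicity correction and tests everything at P<.05, so calling safety primary or secondary changes no alpha level, test or sample size. This also stands. For safety, the mismatch between 1.1 and 10.2 is mostly one of headings; the substance is the absent estimate and interval.

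**Low power in a pilot is not an error.** Agreed. The trial is declared pilot and exploratory. The power figures show only how little a non-significant result says.

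**The randomised comparison is useful.** Infection is common after transplant, so a group 1 rate alone is hard to interpret. The comparison should be kept, as a difference with an interval.

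**Feasibility is not wholly absent.** Section 5.1.6 does mention a separate analysis, and 5.1.7 sets a product minimum. Neither states a proportion or a denominator. A reader might go further and say that the plan must have a feasibility threshold; the documents offer no basis for choosing one.

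**Conclusion.** The point holds in a limited form. Primary objective 2 has no analysis in 10.1. For safety, the plan names three outcomes and a difference test but no estimate or interval. For feasibility, which is the clearer gap, it gives neither a proportion nor a denominator, while 5.1.6 and 5.6 take collection failures out of group 1.

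At 10 per arm and under the assumed rates shown, power to detect an excess of 20 to 40 percentage points is 14% to 47% by uncorrected chi-square and 6% to 30% by Fisher. A non-significant test is therefore weak evidence of safety. The exact upper limit of 31% for 0/10 needs no assumed rate, only that 10 subjects are counted; with 8 it would be 37%.

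This is a worthwhile and inexpensive improvement. It does not show that the trial lacks safety oversight, that its size is wrong for a pilot, or that the sponsor plans to claim safety from P>.05.

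**What to change.** List both items in 10.1 and align 10.2 with 1.1 and 1.2.

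- **Safety.** For each outcome named in 10.2, report the group 1 rate with an exact 95% CI and the between-arm difference with a 95% CI. State that P>.05 is not evidence of safety. If a test is kept, use an exact one, since expected counts will be small.
- **Feasibility.** Among all subjects randomised to group 1, including those removed or transferred under 5.1.6 and 5.6, report the proportion who received both a CD34-selected graft meeting the protocol's own content limit and the day +7 infusion, with an exact 95% CI.
- **Reconcile 5.1.6 and 5.6** on how subjects who miss the collection minimum are handled and followed, so that the all-randomised denominator can be completed. Which handling applies is for the sponsor.
- **Optional.** The sponsor may fix a minimum feasibility count in advance.

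The cost is rewording of Section 10, that reconciliation, and short analysis definitions of engraftment, autoimmune effect and infection, which 10.2 leaves open. The downside is that the safety and feasibility conclusions become visibly imprecise, as they must be with 10 subjects.
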